Protocol Clinical Trial

Title of the project

Tight caloric control (TiCaCO) in the cachectic oncologic patient before the start of cancer therapy can stabilize body weight, thereby reducing morbidity and mortality: validation of the pilot trial. A randomized study.

Objective of the study

In our pilot trial, 20 patients were randomized, 10 receiving regular counseling by regular oncodietitians, while the 10 others received nutrition therapy. In the latter group, an assessment of biophysical parameters was made (including the bioelectrical impedance analysis or BIA for body composition), and their Energy Expenditure was assessed using indirect calorimetry. Afterwards, they received nutrition therapy according to the ESPEN (European Society for Parenteral and Enteral Nutrition) guidelines. Supplementary interventions were made to match caloric intake to energy expenditure (the 'Tight Caloric' approach), using enteral and parenteral nutrition if indicated, by an intensive coaching and follow-up to continue this nutrition strategy (with dieticians even being "on call" after hours). While the study follow-up lasted 2 years, nutrition therapy was only performed during the first 3 months. The results were striking: apart from keeping their body weight in balance, the patients of the nutrition therapy group counted much less unexpected hospitalisation days and they clearly lived much longer (De Waele, Appetite, 2015).

This project targets the validation of these results on a large scale. For this study, patients with either colorectal adenocarcinoma and non-small cell lung carcinoma, due to their high incidence as well as the high prevalence of cachexia in these patients will be included. While patients will be randomized, it is not possible to perform a double- or even single-blinded study due to the nature of the treatment. The recruitment phase will last 2 years, keeping refusals and dropouts in mind. Follow-up will last 2 years after inclusion, although the actual nutrition therapy will again last only 3 months: the period of active oncological treatment. An intermediate analysis is already made after the first year of follow-up. In case survival is already statistically significant, the trial will be stopped for ethical reasons. In case of a positive result, we want to implement nutrition therapy as a standard treatment in cachectic cancer patients in Belgium.

In case of a positive outcome (i.e. mere confirmation of our published results), the major advantage of nutrition therapy will be its relatively low cost while still affecting morbidity and mortality significantly. This can be practically achieved by redefining the dietician's task. The patient's own active participation in the decision making process is an important surplus in well-being and overall treatment. In combination with decreased morbidity and mortality the benefit of the patient can be found on every level.

Investigator(s)

PI and head of department of nutrition:

[name] [name], PhD: [contact]

Intensive Care UZ Brussel

Co-investigator:
[name], PhD: [contact]
Diabetes Clinic UZ Brussel

Sponsor *If applicable*

Baxter
Nutricia

Departments/laboratories involved in the study
Department of Nutrition: [contact]
Department of Intensive Care:
[contact] or [contact]
Department of Oncology: [contact]

Introduction

Background

Cancer is a disease with a high prevalence and incidence worldwide, and often incurable because the diagnosis is made in an advanced stadium. Nevertheless, 50% of patients survive on average 10 years nowadays (accounting for all cancers together). This, however, does not necessarily equals a state of being cured from cancer. On the other end of the spectrum there are patients with a very poor prognosis from the beginning, regardless of treatment. The financial drawback is that the costs for treating cancer worldwide are the highest of any disease, accounting for nearly one trillion euro per year.

One major cause for a poor prognosis is the presence of malnutrition, due to a decreased intake, caused by the patient's symptoms. Symptoms can vary greatly, but are usually of gastrointestinal nature (nausea, vomiting), although general weakness and even depression can be present, all caused by advanced disease itself or by therapy (typically chemotherapy). Advanced disease is also marked by an increased resting energy expenditure, due to the tumor's induction of a hyperkatabolic state of the body. This will cause the clinical entity called "cachexia" and will eventually be responsible for the patient's demise. Although cachexia is usually referred to as a body mass index (BMI) of < 20, in cancer a broader definition is used, whereby a weight loss > 5% over a period of 6 months is sufficient for the diagnosis, regardless of BMI (Fearon K, Nature Reviews Clinical Oncology, 2013).

This is the reason that restoration of the nutritional state of the patient, using nutrition therapy, is regarded as a promising form of supportive treatment of a cancer patient. It had already been shown that restoring the nutritional state will have a positive effect on wellbeing, morbidity, progression-free survival and possibly even overall survival (Rock CL, CA: a cancer journal for clinicians, 2012). Finally, a recent pilot study was able to demonstrate higher overall survival using nutrition therapy, albeit the sample size was small (De Waele, Appetite, 2015).

One major advantage of nutrition therapy is its broad spectrum, being used both enterally and parenterally. Its potential is very large, as its advantages have been demonstrated for a wide array of cancers (depending on the study's setup). Moreover, nutrition can have a preventive role in the incidence of cancer. Nutrition therapy has even been shown to be effective in the

deadliest cancers, such as pancreatic cancer (Pericleous M, Anticancer research, 2014) and lung cancer (Koutsokera A, Clinical lung cancer, 2013). Despite of these results, the pathophysiology is only partly known (Suzuki H, J gastroenterology, 2013).

The strategy of nutrition therapy, however, may vary in the course of disease as both physiological as psychosocial changes can occur. It may easily be possible that a switch to tube feeding or even parenteral nutrition is needed, be it temporally or even permanently. This makes a holistic approach to nutrition mandatory, rather than focus on one or multiple food additives. In this regard, it has been shown that most supplements in monotherapy do not offer a single benefit (Ries A, palliative medicine, 2012).

This project targets the implementation of nutrition therapy in oncologic patients with cachexia, on a large scale. Its setup has been previously described in the domain of Intensive Care (Singer P, Intensive Care Medicine, 2011), and has proven to be fruitful in our pilot study (De Waele, Appetite, 2015).

Rationale

In our pilot trial, 20 patients were randomized, 10 receiving regular counseling by regular oncodietitians, while the 10 others received nutrition therapy. In the latter group, an assessment of biophysical parameters was made (including the bioelectrical impedance analysis or BIA for body composition), and their caloric status was assessed using indirect calorimetry. Afterwards, they received nutrition therapy according to the ESPEN (European Society for Parenteral and Enteral Nutrition) guidelines and supplementary matching caloric intake to energy expenditure (the 'Tight Caloric' approach) by an intensive coaching and follow-up to continue this nutrition strategy (with dieticians even being "on call" after hours). While the study follow-up lasted 2 years, nutrition therapy was only performed during the first 3 months. The results were striking: apart from keeping their body weight in balance, the patients of the nutrition therapy group counted much less unexpected hospitalisation days and they clearly lived much longer (De Waele, Appetite, 2015).

This project targets the validation of these results on a large scale. For this study, patients with either colorectal adenocarcinoma and non-small cell lung carcinoma, due to their high incidence as well as the high prevalence of cachexia in these patients. While patients will be randomized, it is not possible to perform a double- or even single-blinded due to the nature of the treatment. The recruitment phase will last 2 years, keeping refusals and dropouts in mind. Follow-up will last 2 years after inclusion, although the actual nutrition therapy will again last only 3 months. An intermediate analysis is already made after the first year of follow-up. In case survival is already statistically significant, the trial will be stopped for ethical reasons. In case of a positive results, we want to implement nutrition therapy as a standard treatment in cachectic cancer patients in Belgium.

In case of a positive outcome (i.e. mere confirmation of our published results), the major advantage of nutrition therapy will be its relatively low cost while still affecting morbidity and mortality significantly. This can be practically achieved by redefining the dietician's task. The patient's own active participation in the decision making process is an important surplus in well-being and overall treatment. In combination with decreased morbidity and mortality the benefit of the patient can be found on every level.

Study design

randomized controlled double-blind parallel-group multi-centre study

Medication/device *If applicable*

Not applicable (enteral and parenteral nutrition, commercially available)

The subjects

Number of subjects

- Colorectal cancer (CRC) st. III - IV (TNM system) with cachexia
- Non-small cell lung cancer (NSCLC) st. III - IV (TNM system) with cachexia

120 subjects in each group, 60 controls and 60 Nutrition Therapy patients, based on statistical power. 20% extra patients were added to this number to account for dropouts.

Investigational group (Group A)

At the time of diagnosis, patients will immediately be screened and started with Nutrition Therapy if assigned to group A. This regimen will stay in place for 3 months, after which a switch will be made towards normal dietary counselling. Nutrition Therapy can be given orally, parenterally or via tube feeding, depending on the patient's status and aims at matching caloric Intake with Resting Energy Expenditure. Moreover, a switch between these modalities is possible during these 3 months. Afterwards, standard dietary counselling will be given during the remainder of the study. Follow-up will last 1 year. If one year after the last enrolment the study shows a large difference with the control group, the study will be stopped for ethical reasons.

Reference group (Group B)

At the time of diagnosis, patients will immediately be screened and started with standard dietary counselling for 2 years if assigned to group B. Dietary intervention can be orally, parenterally or via tube feeding, depending on the patient's status. Moreover, a switch between these modalities is possible during these 3 months. Follow-up will last 1 year. If one year after the last enrolment the study shows a large difference with the control group, the study will be stopped for ethical reasons.

Both Groups:

Oncological treatment will be performed at the discretion of the participating specialists, following the ESMO guidelines. Although an open label study, the oncologic treatment will not be related to the dietary regimens.

Inclusion is to take place in a period of one year. The duration of the study for each subject from randomisation to end of treatment is three months and a follow up period of nine months, for a total of one year per patient. Afterwards, analysis will take place.

Power calculation:

96 patients per cancer group (48 controls and 48 nutrition therapy), supplemented with 20% per group to take dropouts into account.

Inclusion criteria

- > 18 years
- Male and female
- CRC or NSCLC before chemo- or radiotherapy is started (naive to treatment), but surgery may already have been performed
- CRC or NSCLC relapse > 3 months after initial oncologic therapy
- Oncologic cachexia (undesired weight loss > 5% in less than 6 months)
- Written informed consent / ability to give informed consent

Exclusion criteria

- concomitant second malignancy
- uncertainty of diagnosis of CRC or NSCLC
- patient unfit for chemotherapy
- patient unfit for radiotherapy
- patient unfit for surgery
- palliative treatment or terminal patient (life expectancy < 3 months)
- patient already participating in another study
- Pregnancy / lactation
- Any other pathology present that causes the patient to be unfit for oncologic therapy (e.g. end-stage renal failure, severe COLD, severe heart failure)
- Unable to adhere to protocol instructions (e.g. language barrier)
- Investigator's uncertainty about the willingness or ability of the patient to comply with the protocol requirements
- Participation in any other studies involving investigational or marketed products concomitantly or within two weeks prior to entry into the study

Replacement of subjects

In case of dropout, subjects will be censored on the Kaplan-Meier curves.

[figure not shown]
Restrictions and prohibitions for the subjects

None.

Procedures

See below, to be performed at the oncology consultation.

Flowchart

systematic overview of the study: planned tests per visit of the subjects

Expected total duration of the trial: 2 year (inclusion).

Supervising MD during the tests: Principal Investigator: [name] or co-investigator: [name].

Randomisation/blinding

Computerized randomization, validated for clinical trials, are used.

Prior and concomitant therapy

See "Inclusion and Exclusion criteria". All other concomitant therapy is allowed.

Study analysis

Sample size calculation

The statistical power was calculated based on the pilot trial.

Analysis of the samples

Outcome parameters:

• Body weight
• BIA Bio-Electrical Impedance Analysis
• Blood Pressure
• Blood Sample Analysis
• Caloric and Nitrogen intake
• Indirect Calorimetry
• Sensewear ®
• Body weight
• BIA Bio-Electrical Impedance Analysis
• Blood Pressure
• Blood Sample Analysis
• Indirect Calorimetry
• Body weight, mortality, morbidity.
- Primary: weight stabilisation, morbidity and mortality
- Secondary: Quality of Life (QoL 36)

Statistical analysis

2-tailed, paired t-tests will be used for statistical analysis.

Quality control and quality assurance

The quality control is performed by the certified and experienced research unit of the Intensive Care Department.

Publication policy

All rights belong to the PI and thus to the VUB/the UZ Brussel.

Protocol Amendment dd 12/06/2017

Background:

Due to lack of patients with 5% weight loss in 6 months and, by consequence, very low inclusion rate, it was decided to amend the protocol. To achieve this, a special cooperation with the department of Radiotherapy was established. The service sees many patients who lose weight during radiotherapy, partly because of cancer-related cachexia, but mostly due to the mucositis caused by radiotherapy itself, losing > 10% of their initial body weight (at the start of their therapy). This is especially seen in cancers of head and neck, oesophagus and stomach. Radiotherapy is performed on working days and treatments typically last 5-7 weeks (depending on indication).

Amendment:

- Inclusion of patients with colorectal, lung and pancreatic cancer will be changed to: Inclusion of patients with lung, gastric, oesophageal, head and neck and pancreatic cancer
- 5% weight loss over the past 6 months will be changed to: patients with the aforementioned cancers where radiotherapy will be part of their treatment (or will be the entire treatment)
- Duration of intervention of 3 months will be changed to: duration of intervention for the entire period of radiotherapy
- After recalculation of statistical power, only 48 patients will be needed instead of 96. With correction for dropouts, this will become 60 patients instead of 120. This means 30 controls and 30 patients in the intervention group.
- The amendment will be added to the registration at *clinicaltrials.gov*.

The procedure and flowchart will remain unchanged. Analysis of the data will remain: in whole, per cancer and per sex (the latter two criteria requiring 60 patients in each group).

Protocol Amendment dd 19/09/2017

Background:

The study has seen much more inclusions and is running well thanks to the previous amendment. Due to a typo, the colorectal cancer group was unfortunately omitted. Also, the absolute difference of survival in the TiCaCo trial after one year was similar to that after the second year.

Amendment:

- Colorectal cancer patients are still to be included. Otherwise, nothing changes concerning inclusion criteria.
- The follow-up will be shortened from 2 years to one year.
- The amendment will be added to the registration at *clinicaltrials.gov*.

Protocol Amendment dd 05/02/2019

Background:

The study needs 48 inclusions that remain in the study until the end. However, the number of dropouts is too high, severely compromising the study's statistical power. Therefore, an inclusion surplus of 20 - 25% is required.

Amendment:

- The inclusion period will be expanded to 31/12/2019 or the inclusion of 60 patients (including dropouts), whichever is sooner.
- The amendment will be added to the registration at *clinicaltrials.gov*.

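### Two conflicting efficacy stopping rules survive the cut to one-year follow-up: at the final data they are empty, and at any earlier look they reserve no alpha.

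*Protocol*

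**What the plan says.** The protocol gives two efficacy stopping rules.

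- **Objective of the study, repeated in Rationale.** "An intermediate analysis is already made after the first year of follow-up", followed by "In case survival is already statistically significant, the trial will be stopped for ethical reasons". The endpoint is survival and the criterion is significance, with no level or boundary. The same paragraph says "Follow-up will last 2 years after inclusion".
- **Investigational group (Group A) and Reference group (Group B).** "If one year after the last enrolment the study shows a large difference with the control group, the study will be stopped for ethical reasons". This rule names neither an endpoint nor a threshold.

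The statements on duration also differ. The Objective says "The recruitment phase will last 2 years, keeping refusals and dropouts in mind", while the text under Both Groups says "Inclusion is to take place in a period of one year". That text also gives each patient "three months and a follow up period of nine months, for a total of one year per patient. Afterwards, analysis will take place". The amendment of 19/09/2017 then states: "The follow-up will be shortened from 2 years to one year". None of the three amendments mentions an interim look or a stopping rule.

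Mortality is one of the listed primary outcomes, so a survival look tests part of the primary objective.

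**The concern.** The two rules cannot both be followed. They use different criteria (significance, or an unquantified difference) and different clocks (the first year of follow-up, or one year after the last enrolment).

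Both suit a two-year follow-up, in which data at one year are a midpoint with more to come. Once follow-up is one year, that midpoint becomes the end. Either the look is the final analysis and the rule does nothing, or the look is held earlier and becomes a real efficacy test with no alpha set aside for the final one.

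The Objective says that a positive result should make nutrition therapy standard treatment for cachectic cancer patients in Belgium, so the survival threshold matters. The trial cannot be blinded, according to the same section. An undefined large difference therefore leaves the decision to people who know the allocation.

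**Working it through.** The protocol states no alpha, overall type I error or boundary, so there is no figure of its own to reproduce on this point. The check has two parts.

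**1. When do the looks fall?**

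Let A be the accrual period and F the follow-up per patient, in years. The last patient's data are complete at A + F. The Group A/B look is at A + 1.

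| Source of A and F | A | F | Final data (A + F) | Group A/B look (A + 1) |
|---|---|---|---|---|
| Objective, before amendment | 2 | 2 | 4 | 3 |
| Both Groups | 1 | 1 | 2 | 2 |
| Objective accrual, follow-up as amended 19/09/2017 | 2 | 1 | 3 | 3 |

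Under two-year follow-up the look comes a year before the end. Under one-year follow-up it coincides with the end for any A, because F = 1. The Objective's look, if it means one year of follow-up for each patient, falls at the same point. By then enrolment is closed. The intervention is also over, since the amendment of 12/06/2017 ties it to the radiotherapy course, typically 5-7 weeks. Stopping changes nothing.

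**2. What if a look really precedes the final data?**

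Assumptions: two-sided 5% at each of two looks (the protocol says only that tests are 2-tailed) and information fraction t at the first look. Under no effect, the two test statistics are approximately bivariate normal with correlation √t, so

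overall error = 1 − P(|Z₁| < 1.96 and |Z₂| < 1.96).

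| t (assumed) | √t | P(neither look significant) | Overall error |
|---|---|---|---|
| 0.30 | 0.548 | 0.9107 | 8.9% |
| 0.50 | 0.707 | 0.9169 | 8.3% |
| 0.75 | 0.866 | 0.9266 | 7.3% |

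To see which t is plausible for a look one calendar year after the first enrolment, assume uniform accrual, exponential death, one-year follow-up and one-year survival of 40-80%. The documents give no death rate.

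- One-year accrual: the look holds about 52-58% of the final deaths, and the overall error is about 8%.
- Two-year accrual: it holds about 26-29%, and the overall error is about 9%.

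**Check of possible boundaries, same formula**

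- Stopping only at p < 0.001 (|Z₁| > 3.291), with the final test at 5%: overall error 5.05% at t = 0.3 and 5.02% at t = 0.5.
- O'Brien-Fleming at t = 0.5: nominal levels of 0.0052 at the look and 0.048 at the end hold 5% overall.

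**The case against.** The strongest reply is that no error is inflated. The sentence on the intermediate look directly follows the one setting two years of follow-up, so its natural meaning is the midpoint of that scheme. The amendment removed the scheme. One analysis remains, alpha is spent once, and the stopping text is a leftover. This stands for the per-patient reading, and it is why the 7-9% must be conditional. It does not rescue the rule, which on that reading is obsolete text still in force.

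A second reply is that boundaries are normally left to the statistical analysis plan, and that the word significant is compatible with an adjusted level. A missing boundary alone would indeed be no finding. But the protocol does not defer the matter. It fixes one trigger as significance and another as a large difference, at different times. A boundary elsewhere would not reconcile these.

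A third reply is that amendments appended to a protocol naturally differ from the body. That is so, but the two rules already conflict within the body, and no amendment touches either.

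A reader might infer more than the documents support:

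- **That an early look would rest on very few deaths.** The documents give no death rate, so the number is unknown.
- **That the chance of a false claim is about 17%, counting all three primary outcomes.** At an assumed correlation of 0.3, about 13.5 of those points come from testing three outcomes, without any interim look. The look adds about 3. The total also assumes that success on any one outcome counts, which the protocol does not say.
- **That a look falls after the final data.** Under one-year follow-up none does; they coincide.

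**Conclusion.** The point holds as an unreconciled and faulty decision rule. The conflict of criterion and timing, and the failure to revise the rules in the amendment of 19/09/2017, can be read from the text and need no assumption. That the Group A/B look coincides with the final data follows from one-year follow-up alone, whatever the accrual period.

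The error inflation is conditional. It arises only if the Objective's look is held before the final data. It is then from 5% to about 7-9% for survival, resting on an assumed two-sided 5% and assumed information fractions of 0.75 to 0.3. A reader might conclude that the trial's type I error is inflated as planned. The documents do not support that, because on the per-patient reading there is only one analysis.

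On no reading is the rule as written both operative and error-controlling. It should be settled before survival data are examined.

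**What to change.** Reconcile the Objective, the Rationale, the Group A and Group B sections and the amendment of 19/09/2017 on follow-up length, timing of any look and stopping criterion. The simplest way is to delete both stopping rules and state one survival analysis, one year after the last inclusion, at a stated alpha.

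If the sponsor wants an earlier look, state when it occurs and give one boundary on the survival test that controls alpha, in place of both present criteria. Haybittle-Peto at p < 0.001 would leave the final test at essentially 5%. An O'Brien-Fleming boundary is an equally acceptable choice, with the final level adjusted accordingly.

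The cost is protocol wording only. The downside is that early stopping for efficacy becomes less likely, or is given up if no look is kept.

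### Mortality is a primary outcome, but the one test the protocol fixes is a paired t-test, which leaves out disease stage and treatment-naive/relapsed status, both known at entry and mixed among 60 patients

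*Protocol*

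**What the plan says.** Under Outcome parameters the protocol lists "Primary: weight stabilisation, morbidity and mortality". Under Statistical analysis the whole method is "2-tailed, paired t-tests will be used for statistical analysis". Survival curves are mentioned once, under Replacement of subjects: "In case of dropout, subjects will be censored on the Kaplan-Meier curves". No survival test, model, covariate or stratum is given.

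Two prognostic mixtures are written into eligibility:

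- **Stage.** Number of subjects lists "Colorectal cancer (CRC) st. III - IV (TNM system) with cachexia" and "Non-small cell lung cancer (NSCLC) st. III - IV (TNM system) with cachexia".
- **Disease status.** Inclusion criteria admit treatment-naive patients and also "CRC or NSCLC relapse > 3 months after initial oncologic therapy".

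The allocation sentence, "Computerized randomization, validated for clinical trials, are used", names no stratification factor. The amendment of 12/06/2017 reduces the trial to 60 patients (30 per arm) and adds tumour sites. It keeps analyses overall, by cancer and by sex, but none by stage or disease status. The amendment of 19/09/2017 restores colorectal cancer, which makes six sites, says the inclusion criteria otherwise stay as they are, and cuts follow-up to one year. The amendment of 05/02/2019 ends recruitment at a fixed date or at "the inclusion of 60 patients (including dropouts), whichever is sooner".

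**The concern.** A protocol that left covariates to a statistical analysis plan would give no cause for comment. This one names its method, and that method has no place for a covariate and no way to handle censored times. Two factors that define the population, and are therefore on record at entry, go unused in the comparison of a primary outcome.

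Two things are at stake. With 30 per arm, a chance surplus of stage IV or relapsed patients in one arm can create or hide an apparent survival difference in the one allocation that will be reported. And leaving out a strong prognostic factor pulls the hazard ratio (HR) towards 1 and lowers power, which is already low here. The survival result also carries weight during the trial, because the Objective section would stop the trial if survival is significant at the intermediate analysis.

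**Working it through.** **The plan's own size.** 48/(1 − 0.20) = 60 and 96/(1 − 0.20) = 120, so both enrolment figures follow from the stated 20% dropout. The base figures 48 and 96 cannot be rebuilt, because the protocol gives no effect size, event rate, alpha or power. The inputs below are 30 per arm (24 if only completers count) and one year of follow-up, from the amendments. The rest are assumptions.

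**Chance imbalance in stage.** Let p be the stage IV share, with an independent Binomial(30, p) count per arm. The between-arm difference in share has SD √(2p(1 − p)/30). A gap of 20 points is 6 of 30 patients.

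| Assumed p | SD of difference | P(gap ≥ 20 points) |
|---|---|---|
| 0.50 | √(2 × 0.25/30) = 0.129 | 15.5% |
| 0.30 | √(2 × 0.21/30) = 0.118 | 12.0% |
| 0.20 | √(2 × 0.16/30) = 0.103 | 7.5% |
| 0.10 | √(2 × 0.09/30) = 0.077 | 1.8% |

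With 24 per arm the 50% and 30% rows become 19.3% and 15.5%.

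**What an imbalance does.** The paired t-test has no natural application to censored survival in two independent arms, so an arm-only Cox model stands in for the unadjusted comparison. Survival is exponential, censored at one year, with half the patients stage IV. With no true effect, among trials where one arm has at least 20 points more stage IV, the median unadjusted HR against that arm is 1.22 to 1.36 for a stage HR of 2 to 4. The stage-adjusted HR is about 1.0.

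**Over all allocations.** With no true effect, type I error is 4.0% to 5.0% unadjusted and 5.1% to 5.3% adjusted.

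**Power, two-sided 5%, half the patients stage IV.** Rows giving a relapse HR assume 30% relapsed and 50% one-year control mortality, and adjust for both factors. The others adjust for stage only.

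| Per arm | Treatment HR | Stage HR (relapse HR) | Unadjusted | Adjusted | Gain, points |
|---|---|---|---|---|---|
| 24 | 0.5 | 1 (1) | 28.9% | 29.6% | 0.7 |
| 24 | 0.5 | 2 (1.5) | 28.2% | 30.4% | 2.2 |
| 24 | 0.5 | 3 (2) | 26.3% | 30.7% | 4.4 |
| 30 | 0.5 | 3 (2) | 30.8% | 37.9% | 7.1 |
| 30 | 0.4 | 2 | 56% | 58% | 2 |
| 30 | 0.4 | 3 | 55% | 62% | 7 |
| 30 | 0.4 | 4 | 51% | 62% | 11 |
| 30 | 0.4 | 4, control mortality 70% | 59.4% | 74.3% | 14.9 |

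These settings give 3000 trials each. The last row, with about 34 deaths, marks the upper end of the range. At 50% control mortality and treatment HR 0.5, about 19 to 24 deaths are expected.

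**The case against.** The strongest reply is that covariate choice belongs in a statistical analysis plan, which is not at hand, and that nothing in the protocol says mortality will go unadjusted. The second half is correct. A reader might infer that mortality will be shown only on unadjusted Kaplan-Meier curves and that allocation is simple and unrestricted. The documents support neither: the Kaplan-Meier sentence is a censoring rule, and the randomisation sentence does not describe the scheme. What the reply does not remove is the sentence that fixes a paired t-test, a stated choice that cannot carry these factors.

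Other objections stand in part:

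- **Chance imbalance is not bias.** This stands. The unadjusted test holds its level, and the HRs of 1.22 to 1.36 describe selected, imbalanced trials.
- **The inputs are not in the protocol.** This stands, so the results are given as ranges. Excluding palliative treatment and patients unfit for therapy may lower the stage IV share. At 10%, a large gap is rare (1.8%).
- **Stage III–IV is stated only for colorectal and non-small cell lung cancer.** This stands, and stage must be defined for the added sites. It does not remove the mixture, since no amendment withdraws the stage range or the relapse criterion.
- **Tumour site is a further source of mixed prognosis.** This stands. Six sites in 60 patients average 10 each, and a stage term will not absorb that. It limits what adjustment achieves but is no reason to leave stage out.

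**Conclusion.** The point holds as one of efficiency and robustness. The protocol fixes, for a primary outcome that includes mortality, a test that cannot use two prognostic factors known at entry. With 30 per arm, a stage IV gap of 20 points or more has a probability of about 7% to 16% (assumed share 20% to 50%). Leaving stage out costs about 0 to 15 points of power (assumed stage HR 2 to 4, treatment HR 0.4 to 0.5); the loss is near zero if the factors barely matter and largest with strong factors and many deaths.

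A reader might go further and conclude that the mortality result will be biased, or that imbalance is certain to go uncorrected. Neither follows: type I error stays near 5%, and a separate analysis plan could still add adjustment. If it does, it will have to contradict the t-test sentence, which is a reason to correct the protocol itself.

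**What to change.** Under Statistical analysis, withdraw the paired t-test for mortality and state:

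> Mortality is compared between randomised arms with a Cox model including arm, TNM stage at entry (III or lower / IV) and disease status (treatment-naive / relapse). Kaplan-Meier curves are for display.

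Define the stage categories for all six tumour sites before analysis. Do not let the number of deaths switch the method: a threshold such as 20 deaths lies inside the plausible range, so one or two events could decide the test.

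The cost is a short amendment and a slightly longer analysis, with no new patients and no data beyond those recorded at entry. The limit is the event count. With about 20 to 35 deaths only one or two covariates can be carried, so if one must be dropped, keep stage, and say so in advance.
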